8.3 ECHOCARDIOGRAPHIC EXAMINATIONS

Each sonographer participating in the clinical investigation must be trained on the requirements of the Echo Manual.

⁸ Bioprostheses must be returned to the Sponsor. It is preferable that delivery systems are returned also, but they may be discarded as described in the IFU.

8.4 DOCUMENTATION

Training will be documented on a training record provided by the Investigation Sponsor, which the trainee must sign and date. The training of investigation support staff must be completed and documented before the staff member may perform the specific clinical investigation related tasks delegated to them by the Principal Investigator.

9 PROCEDURES AND METHODS

9.1 BASELINE EVALUATION

The Phase I or Phase II baseline evaluation will include:

- 1. Initial screening for the clinical inclusion and exclusion criteria,
- 2. Informed consent discussion and dated signature
- 3. History and physical examination,
- 4. Baseline blood studies per protocol, Section 9.1.3
- 5. Baseline transthoracic echocardiogram (TTE) per protocol (Section 9.5)
- 6. Baseline 12 lead electrocardiogram
- 7. NYHA Functional Class
- 8. Quality of Life Survey (EQ-5D)

9.1.1 SUBJECT SCREENING

All subjects diagnosed with aortic stenosis requiring aortic valve replacement seen by cardiac surgeons participating in this clinical investigation should be screened for eligibility. All subjects who meet eligibility requirements will be asked to participate. A Screening Log will be provided to the investigational centers to maintain a cumulative log of all screened subjects admitted for aortic valve replacement by the cardiac surgeons participating in this investigation. For subjects listed as not eligible for participation in the clinical investigation, a reason supporting the disqualification of the subject must be entered on the screening log. The Screening Log shall be duly completed and faxed to the Investigation Sponsor regularly (at least once per month). Any subject deemed ineligible due to active endocarditis, recent myocardial infarction, pregnancy or lactating, or due to participation in another clinical investigation may be re-screened at a later time. Re-screened subjects must be re-entered on the Screening Log.

9.1.2 INFORMED CONSENT

Subjects who are eligible for participation in the clinical investigation shall be provided at a minimum with the following explanation:

- 1. background of the clinical investigation;
- 2. potential benefits and risks of the procedures involved;
- 3. follow-up visit requirements per the clinical investigation.

Each subject shall be given ample time to read the Informed Consent in its entirety and ask questions to make an informed decision. The subject must sign and date the investigational center's Ethics Committee (EC) approved Informed Consent before any clinical investigation specific procedure is applied to the subject. Subjects who provide

informed consent will be assigned a unique investigation subject identification number that will be recorded on the Screening Log. The Investigator, or designee, and any witnesses shall also sign and date the consent form, as indicated. Failure to provide Informed Consent renders the subject ineligible for participation in the clinical investigation including undergoing treatment with the investigational devices. Subjects who do not provide informed consent also are recorded on the Screening Log.

For subjects who are not able to read or write and or are blind, a legal representative who is authorized to sign and date the consent on the subject's behalf will do so, but only after the informed consent is read and explained, all questions answered and understood by the subject and legal representative and the subject has given verbal agreement to volunteer for the clinical investigation. An independent witness (other than the subject's legal representative or the consenting physician) shall be present throughout the process. A note will be made of the subject's verbal agreement to participate; furthermore the witness shall also sign and personally date the informed consent form attesting that the information was accurately explained and that informed consent was freely given.

9.1.3 BASELINE ASSESSMENT

After a written informed consent has been obtained from the subject the following baseline tests and exams will be conducted: transthoracic echocardiography (TTE) per protocol (Section 9.5); 12-lead electrocardiogram; blood studies per protocol; an assessment per NYHA Functional Classification; completion of a Quality of Life Survey (EQ-5D); a pregnancy test (not applicable if subject is male or female who is post-menopausal / surgically sterile). Test results conducted within 30 days before aortic valve surgery may be used for this investigation if all values per protocol are available. Baseline information to be documented is further detailed in Table 1.

General information	Clinical information	Blood studies	Echocardiography ⁹
Birth Date	Cardiac Rhythm (12-	Blood Draw Date	Date of exam
Subject Sex	lead EKG)	White Blood Cell	2D measurements
Height	NYHA Classification	Count	Ejection fraction
Weight	Cardiovascular Risk	Red Blood Cell Count	Aortic bioprosthesis
Heart rate	Factors	Hemoglobin	assessment
	Cardiovascular	Hematocrit	LVOT assessment
	Conditions	Haptoglobin	Mitral Valve
	Previous Procedures	Reticulocytes	assessment
	/ Interventions	Platelet Count	Other Variables
	Non-Cardiovascular	Serum Lactate	Left Ventricular
	Conditions	Dehydrogenase	Assessment
	Quality of Life		

 Table 1: Baseline Assessment

9.2 SURGICAL PROCEDURE

9.2.1 PROCEDURE PREPARATION

The surgical approach used will be at the discretion of the investigator in his/her routine surgical practice. At the time of aortic valve replacement a transesophageal echocardiogram to further assess the anatomy (See Intra-operative Exclusion criteria section 6.3) is recommended prior to aortic valve replacement with the EDWARDS INTUITY Aortic Valve. After performing the aortotomy, the native valve and surrounding anatomy should be examined for compatibility with the devices (See Intra-operative Exclusion criteria section 6.3).

9.2.2 EDWARDS INTUITY AORTIC VALVE IMPLANTING PROCEDURE

A detailed description of device preparation and use is provided in the Instructions for Use (IFU) of both Models 8300ACA and 8300ACB, (See Clinical Investigator's Brochure). Investigators must be familiar with Precautions and Technique information described in the IFU prior to use of the bioprosthesis and the delivery system. The EDWARDS INTUITY Valve System implanting procedure uses one bioprosthesis and one delivery system. A second attempt, with new devices, is permitted. If the second attempt is not successful, no further attempts are permitted and the subject should be treated with another surgical valve.

A Transesophageal echo (TEE) should be performed after the bioprosthesis is implanted to assess placement, potential paravalvular leak, and mitral valve function.

Procedural information, findings, results and device identification information to be recorded is identified in Table 2.

⁹ Data evaluation to be performed by a Core Lab as described in the Echo Manual.

General information	Clinical information	Device performance
Date of Admission Date of Procedure Implanting Surgeon Type of Operation	Etiology Diagnosis for replacement Valve implantation Condition of the native aortic valve Sizing Concomitant procedures Intraoperative Adverse Events	Bioprosthesis size and serial number Delivery system size, lot, and components used Device technical success

Table 2: Procedural information

9.3 SUBJECT ENROLLMENT

Subjects will be considered enrolled into the clinical investigation after meeting all the enrollment criteria, signing the informed consent, and after the surgeon sizes the aortic annulus, and determines that the bioprosthesis can be implanted. The point of enrollment in Phase I and Phase II of the clinical investigation is established in the Operating Room when the investigator sizes the aortic annulus and confirms that the subject is an appropriate candidate for the investigation device(s)¹⁰. All subjects enrolled in this clinical investigation must be followed as described in section 9.4 and section 9.5

Adverse events are collected from the time the subject provides consent.

9.4 POST-PROCEDURE

9.4.1 POST-PROCEDURE CARE

Bioprosthetic heart valve recipients should be maintained on anticoagulant therapy (except when contraindicated) during the initial healing stages after implantation, approximately 2 to 3 months in accordance with the ACC/AHA 2006 Guidelines for the Management of Patients with Valvular Heart Disease [8]. Anticoagulants should then be discontinued over a period of 10 days, except in those subjects for whom ongoing anticoagulant protection is indicated, i.e., in the absence of sinus rhythm and in subjects with a dilated left atrium, calcification of the atrial wall, history of previous atrial thrombus, or any other medical condition requiring anticoagulation therapy. However, the appropriate anticoagulation therapy must be determined by the physician on individual basis.

It is recommended to collect post-operative telemetry on all subjects for a minimum of five (days) after aortic valve replacement.

9.4.2 DISCHARGE

A clinical evaluation of Phase I or Phase II subjects, including an echocardiogram (refer to Section 9.5), will be performed at the time of hospital discharge. Medical information, findings, and results to be recorded are identified in Table 3.

¹⁰ The bioprosthesis and the delivery system must be used.

General information	Clinical information	Echocardiography ¹¹
Date of Discharge	Weight	Date of exam
	Heart rate	2D measurements
	Cardiac Rhythm (12-lead EKG)	Ejection fraction
	Anti-thromboembolic therapy	Aortic bioprosthesis assessment
	Adverse Events	LVOT assessment
	Coagulation Profile	Mitral Valve assessment
		Other Variables
		Left Ventricular Assessment

Table 3: Discharge Evaluation

Subjects, who are not discharged within 10 days post procedure must have an echocardiogram (refer to Section 9.5) to further assess placement and performance of the bioprosthesis. This echocardiogram is required to complete the evaluation of procedural success. Those subjects will not require an additional echocardiogram at discharge.

9.4.3 FOLLOW-UP ASSESSMENTS

Post-procedure clinical evaluation will be performed on all Phase I or Phase II of enrolled subjects at 1 month, 3 months, 1 year and annually thereafter until 5 years of follow-up is achieved. The follow-up windows are listed in Table 4.

Follow-up Assessment ¹²	Assessment Window
1-month	± 1 week
3-months	+ 1 month
1-year	± 1 month
2-year	± 1 month
3-year	± 1 month
4-year	± 1 month
5-year	± 1 month
5-year	± 1 month

Table 4: Follow-up Windows

During the Phase I 1-month evaluation of the subject a 12 lead electrocardiogram and a Transthoracic echocardiography (TTE) per protocol (Section 9.5) is required. Medical information and findings to be recorded are identified in Table 5.

¹¹ Data evaluation to be performed by a Core Lab as described in the Echo Manual.

 $^{^{12}}$ 1 week = 7 days; 1 month = 30 days; 3 months = 90 days; 1 year = 365 days.

	_	
General information	Clinical information	Echocardiography ¹³
Date of Evaluation	Cardiac Rhythm	Date of exam
	Weight	2D measurements
	Heart rate	Ejection fraction
	Adverse Events	Aortic bioprosthesis
		assessment
		LVOT assessment
		Mitral Valve assessment
		Other Variables
		Left Ventricular Assessment

 Table 5: Phase I Follow-up Evaluation at 1 Month

During the Phase II 1-month evaluation subject will be contacted to assess his/her current status. Medical information and findings to be recorded are identified in Table 6. It is acceptable to obtain the information through an evaluation conducted via telephone. Should the subject return, for any reason, to the investigational center for the Phase II 1-month evaluation, assessments of the cardiac rhythm, weight, heart rate, NYHA functional classification and a Transthoracic echocardiography (TTE) are requested.

Table 6: Phase II Follow-up Evaluation at 1 Month

General information	Clinical information	
Date of Evaluation	Adverse Events	

During the subsequent 3 months, and annual visits, for Phase I or Phase II of the study, the subject returns to the investigational center for the evaluations listed in Table 7

At each postoperative assessment, the investigator(s) will determine the subject's availability for future follow-up visits. If any subject is seen at a time other than a regularly scheduled follow-up visit (called an interim visit), the same information as described in Table 7 will be collected and documented by the investigator.

¹³ Data evaluation to be performed by a Core Lab as described in the Echo Manual.

General information	Clinical information	Blood studies	Echocardiography ¹⁴
Date of Evaluation	Cardiac Rhythm	Blood Draw Date	Date of exam
	Physical Assessment	White Blood Cell	2D measurements
	NYHA Classification	Count	Ejection fraction
	Coagulation Profile	Red Blood Cell Count	Aortic bioprosthesis
	Anti-thromboembolic	Hemoglobin	assessment
	therapy	Hematocrit	LVOT assessment
	Adverse Events	Haptoglobin	Mitral Valve
	Quality of Life (at 3-	Reticulocytes	assessment
	months and 1-year)	Platelet Count	Other Variables
		Serum Lactate	Left Ventricular
		Dehydrogenase	Assessment

Table 7: Follow-up evaluations

9.5 ECHOCARDIOGRAM

All echocardiograms will be independently analyzed by the Echocardiography Core Lab as described in the Echo Manual **Constitution**. Each investigation echocardiogram is to be recorded individually on a computer disc (CD) with the individual subject investigation number provided on the examination screen.

9.6 DEVICE REMOVAL / EXPLANT PROCEDURE

Subjects with device removal or explant will be followed as described in section 9.4 and section 9.5; however neither echocardiography nor blood tests will be performed after discharge, unless required to better assess subject's health status.

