9.6.1 INTRA-OPERATIVE REMOVAL

Intra-operative removal is the excision of the investigation bioprosthesis before the EDWARDS INTUITY Valve System procedure was completed. The heart was not restarted with the bioprosthesis implanted. During the aortic valve replacement (AVR) procedure, should removal of the bioprosthesis be required after the frame was expanded, use of a nerve hook is recommended. Using a scalpel the operator shall carefully cut the bioprosthesis holder retaining sutures and remove the complete delivery system. Then, insert the nerve hook through the outflow aspect of the bioprosthesis. Operator is to engage the expanded frame with the nerve hook and gently pull the frame inward. Then, operator is to disengage the collapsed portion of the frame inwards. The expanded frame at another location, gently pulling the frame inwards. The expanded frame should be engaged and collapsed at least at 3 radial locations. Once the frame is collapsed, the operator shall cut the nadir sutures and remove the bioprosthesis with forceps.

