12.4 PHASE II ANALYSIS

12.4.1 ANALYSIS POPULATION

The primary safety analysis will include all the enrolled subjects including those enrolled in Phase I. The performance analysis will include the subjects who survived at least 30 days post implant.

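### Read literally, Section 9.6 waives scheduled post-discharge echo and blood tests for subjects who carry a second study valve

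*Combined protocol and SAP*

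**What the plan says.** Section 9.6 sets follow-up after a removal or explant. It opens with the general rule and then narrows it: "Subjects with device removal or explant will be followed as described in section 9.4 and section 9.5; however neither echocardiography nor blood tests". In full, the narrowing reads: "however neither echocardiography nor blood tests will be performed after discharge, unless required to better assess subject's health status". It places no condition on which valve, if any, the subject ends up with.

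Section 9.6.1 supplies the definition: "Intra-operative removal is the excision of the investigation bioprosthesis before the EDWARDS INTUITY Valve System procedure was completed". It adds that the heart was not restarted with that valve in place. Explant (Section 9.6.2) is the contrasting case, in which the heart had been restarted.

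Section 9.2.2 deals with a failed first attempt: "A second attempt, with new devices, is permitted". A non-study valve follows only after a second failure: "If the second attempt is not successful, no further attempts are permitted and the subject should be treated with another surgical valve".

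For the 3-month and annual visits, Section 9.4.3 says that "the subject returns to the investigational center for the evaluations listed in Table 7"; Table 7 includes echocardiography and blood studies. On analysis, Section 12.4.1 says: "The primary safety analysis will include all the enrolled subjects including those enrolled in Phase I". The performance analysis takes 30-day survivors, and Section 12.4.4 uses available data without imputation.

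**The concern.** A waiver of valve imaging makes sense once the study valve is gone. Section 9.6 is keyed to the event of removal instead. A subject can have a removal and still go home with a study valve, because a second one may be implanted in the same operation. A site that follows the text as written would not schedule echo or blood tests for that subject after discharge.

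The data at stake serve named endpoints. Study valve paravalvular leakage is a primary safety endpoint and hemolysis a further safety endpoint (Section 5.1). Mean gradient, effective orifice area and regurgitation are performance endpoints at each scheduled visit (Section 5.2). Haptoglobin, reticulocytes and lactate dehydrogenase are scheduled blood data (Section 5.3). The subject stays in the safety population and, if alive at 30 days, in the performance population. A late silent leak would then enter the summaries as no event, and the subject would be absent from the 1-year tests. The missingness would follow from a failed first attempt, so it could not be assumed to be random.

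**Working it through.** The plan states no figure on this point, so there is none to reproduce. The check is textual, followed by a scale calculation on assumed rates.

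**Text, step by step**

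1. *Does a first valve excised before a second attempt count as removal?* Yes under Section 9.6.1: the procedure was not complete and the heart had not been restarted with that valve.
2. *Can the same subject then carry a study valve?* Yes under Section 9.2.2. The switch to another surgical valve comes only after the second attempt fails.
3. *Does Section 9.6 exempt such a subject from the waiver?* No. Its only exception is clinical need.
4. *Does another section restore the schedule?* Sections 9.3 and 9.4.3 apply follow-up to all enrolled subjects. Section 9.6 repeats that rule and then cuts it back for this group, so the specific rule governs. Section 9.8 does not address it.
5. *Is the group foreseeable?* Yes. Section 5.2 defines device technical success as one bioprosthesis with one delivery system, so a second-attempt recipient fails technical success while still carrying a study valve.

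**What continues:** the post-implant TEE (Section 9.2.2), the discharge or day-10 echo (Section 9.4.2), clinical visits, NYHA class, adverse event reporting, and tests needed clinically.

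**Scheduled tests lost per subject**

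- Echo: 6 under Section 9.4.3 and Table 7 (3 months and years 1 to 5), or 4 under Section 12.4.3 (6 months and years 1, 3 and 5). A Phase I subject would also lose the 1-month echo.
- Blood: 3 under Section 5.3 (3 months, 1 year, 5 years). Section 12.4.2 also gives 3, with 6 months in place of 3 months.

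**Scale.** Enrollment is 10 + 340 = 350 (Section 4.2). The share *f* carrying a second study valve after a removal is not given; 1%, 3% and 5% are assumptions.

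| *f* | Subjects = 350 × *f* | Echoes lost (×6 / ×4) | Blood draws lost (×3) |
|---|---|---|---|
| 1% | 3.5 | 21 / 14 | 10.5 |
| 3% | 10.5 | 63 / 42 | 31.5 |
| 5% | 17.5 | 105 / 70 | 52.5 |

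**Sensitivity of a leak proportion.** Assume leak risk is 2% in other subjects and *r* in this group, and that none of this group's leaks is detected. That is a ceiling, because the retained echoes and clinical detection would find some.

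True proportion = (1 − *f*) × 2% + *f* × *r*. Share of leaks missed = *f* × *r* / true proportion.

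| *f* | *r* = 2% | *r* = 10% | *r* = 20% |
|---|---|---|---|
| 1% | true 2.00%, missed 1% | true 2.08%, missed 4.8% | true 2.18%, missed 9.2% |
| 3% | true 2.00%, missed 3% | true 2.24%, missed 13.4% | true 2.54%, missed 23.6% |
| 5% | true 2.00%, missed 5% | true 2.40%, missed 20.8% | true 2.90%, missed 34.5% |

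With *r* = 10% or 20%, the number of leaks missed (350 × *f* × *r*) runs from 0.35 to 3.5. With *r* = 2%, a proportion among scanned subjects is unbiased. If the unscanned stay in the denominator as event-free, the observed value is 1.98%, 1.94% or 1.90% against a true 2.00%.

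**The case against.** The strongest reply is that removal and explant, read together, describe subjects who end up without the study valve. Section 9.6.1 says the heart was not restarted with the valve implanted, whereas a second-attempt recipient's heart is restarted with a study valve. The waiver was probably meant for subjects with no study valve. This stands as a reading of intent. It does not settle the text, because the sentence is still true of the excised first valve and no passage separates the two situations.

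A second reply is that leak detection is largely kept. This stands in part. The TEE and the discharge or day-10 echo can show a leak present at re-implantation, and the within-30-day percentage in Section 12.4.2 rests mainly on them. They do not replace scheduled later data for the late linearized rates, the Kaplan-Meier estimates or the 1-year hemodynamic tests. The clinical-need exception depends on someone recognising a need, so it does not restore systematic data either.

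A reader might infer that every such subject had a frame expanded and collapsed in the annulus and so carries a higher leak risk. The documents do not support that. Section 9.6.1 describes collapsing the frame for removal after expansion, but its definition also covers removal before expansion. No passage gives a leak or hemolysis risk for a second valve.

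**Conclusion.** The gap is real and goes beyond missing detail: a stated rule, followed as written, withdraws scheduled testing from a subject with an implanted study valve who remains in the analysis populations. What is lost is scheduled post-discharge echo and blood data, not all leak or hemolysis follow-up.

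The documents give neither the number affected nor the size of any bias. The figures of about 4 to 18 subjects, and the leak shares in the table, rest entirely on assumed rates. If leak risk after a second attempt is higher, late silent leaks would be under-counted and the reported rate would look better than it should. If it is not higher, the bias is little or none, though the hemodynamic and hemolysis data are still missing. A reader might conclude that the rule is shown to favour the device by a definite percentage; the documents do not support that.

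The change is worth making because it touches a primary safety endpoint and is cheap, even if few subjects prove to be affected.

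**What to change.** Reconcile Section 9.6 with Sections 9.2.2, 9.3 and 12.4.1:

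- Limit the waiver in Section 9.6 to subjects with no study valve in place, and keep its existing clinical-need exception.
- State that a subject implanted with a study valve at a second attempt follows the same scheduled echo and blood assessments as any other implanted subject.
- State in Section 12.4.3 that these subjects are summarized under the size of the valve finally implanted. Section 12.4.1 does not exclude them, so no change of population is needed.

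The cost is a sentence or two. A few subjects receive tests already scheduled for every other implanted subject, at visits they attend anyway, and no extra subjects are needed. The reported leak rate may become slightly less favourable.
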